#### LIST OF ABBREVIATIONS

AE Adverse event

AESI Adverse event of special interest

ALT Alanine aminotransferase AST Aspartate aminotransferase

BMI Body mass index

CFR Code of Federal Regulations

CR Complete response CT Computed tomography

CYP Cytochrome P

(e)CRF (electronic) case report form ECOG Electronic data capture

EDC Eastern Cooperative Oncology Group

EMA European Medicines Agency

EQ-5D EuroQoL

GCP Good Clinical Practice

GPP Good Pharmacovigilance Practices

GSK GlaxoSmithKline

HIFα Hypoxia-inducible factor alphaHRQoL Health related quality of life

ICH International Committee on Harmonization

ICMJE International Committee of Medical Journal Editors

IEC Independent ethics committee

IFN Interferon

ISPE International Society for Pharmacoepidemiology

MRI Magnetic resonance imaging

NA Not applicable NE Not evaluable

ORR Overall response rate
OS Overall survival
PD Progressive disease

PDGF Platelet-derived growth factor PFS Progression-free survival

PR Partial response QD Once daily

RAP Research Analytic Plan RCC Renal cell carcinoma RDI Relative dose intensity

RECIST Response Evaluation Criteria for Solid Tumors

SAE Serious adverse event

SD Stable disease

TKI Tyrosine kinase inhibitor

VEGF Vascular endothelial growth factor

VHL von Hippel-Lindau

# **Trademark Information**

Trademarks of the GlaxoSmithKline group of companies		
VOTRIENT		

Trademarks not owned by the GlaxoSmithKline group of companies
Afinitor
Avastin
Inlyta
Nexavar
Sutent
Toricel

#### PROTOCOL SUMMARY

#### **Rationale**

Although the recently available targeted therapies have provided important improvements in disease prognosis for RCC, for some of these therapies adverse effects may affect tolerability and substantively impact patient quality of life. The availability of alternative treatments that offer similar (or improved) effectiveness with a more favourable safety and tolerability profile remains an unmet need for patients with advanced/metastatic RCC.

While the safety and efficacy of pazopanib has been evaluated in a pivotal randomized, double-blind, placebo-controlled, multinational trial [Sternberg, 2010] and other clinical studies, real-world data are needed to further evaluate the safety, tolerability and effectiveness of this selective tyrosine kinase inhibitor therapy. This is of particular importance for evaluating patient groups that were under-represented in the registration study, e.g., the elderly, patients with co-morbidities, as well as for determining patient compliance outside the normal parameters of a controlled trial.

The purpose of the PRINICIPAL study is to evaluate the real world effectiveness and safety of pazopanib in patients with advanced and/or metastatic RCC.

# Objective(s)

The primary objectives of the PRINCIPAL study are:

- 1. To evaluate overall survival (OS), progression-free survival (PFS) and the overall response rate (ORR) in patients treated with pazopanib;
- 2. To characterise the relative dose intensity (RDI) and its observed effect on treatment outcomes;
- 3. To characterise the RCC patient population treated with pazopanib (e.g., by demographics, disease characteristics, previous RCC treatment history) in comparison to a selected clinical trial population;
- 4. To evaluate the change in health-related quality of life (HRQoL) relative to baseline in patients treated with pazopanib; and
- 5. To evaluate the frequency of serious adverse events (SAEs) and adverse events of special interest (AESIs) in patients treated with pazopanib.

The secondary objectives of the PRINCIPAL study are:

- 1. To evaluate clinical effectiveness, safety and RDI in those patients treated with pazopanib with comparable baseline characteristics to those included in the Phase III clinical trial [VEG105192];
- 2. To evaluate clinical effectiveness, safety, RDI and HRQoL in relevant subgroups treated with pazopanib.

# Study Design

This is a global, multi-centre, long-term, prospective, observational study to evaluate treatment patterns and clinical outcomes in patients with advanced or metastatic clear cell or predominantly clear cell RCC treated for the first time with pazopanib. The study is designed to enroll approximately 700-1000 patients over the course of an enrollment period of approximately 18 months. To the extent possible, consecutive patients meeting inclusion/exclusion criteria will be enrolled.

There are no protocol—mandated visits or procedures associated with the study. Each patient is expected to participate for a maximum of 30 months or until premature discontinuation (i.e., due to death, withdrawal of consent, lost to follow-up or study termination). Follow-up information will be collected approximately every 3 months (a window of  $\pm$  4 weeks around the date of the suggested data collection will be allowed). It is anticipated that the frequency of patient assessment and imaging will differ according to local standard practice; therefore the quarterly data collection time points are intended to collect all assessments (with the date of assessment) since the previous visit date.

# **Study Assessments**

As an observational study, no visits, scans or procedures at enrollment and during followup are required or recommended per protocol. It is expected that evaluations such as bone and brain scans will be performed as clinically indicated (e.g., presentation of bone pain).

The primary effectiveness measures of this study are:

- Overall survival (OS): defined as the time from first treatment with pazopanib until death due to any cause;
- Progression free survival (PFS): defined as the interval between the date of first treatment with pazopanib and the earliest date of disease progression (by tumour response assessed by imaging or by clinical deterioration, whichever comes first) or death due to any cause;
- Overall Response Rate (ORR): defined as the percentage of patients with documented response [complete response (CR) or partial response (PR)] at any time.

The primary safety events of interest in the study are serious adverse events (SAEs) and the following adverse events of special interest (AESI):

- Any adverse event that results in a pazopanib dose modification or discontinuation
- Any other reports of the following AEs, regardless of seriousness or severity:
  - Evidence of liver toxicity
  - New onset or worsened hypertension
  - Cardiac dysfunction
  - Thyroid dysfunction

In addition to these effectiveness and safety parameters, the relative dose intensity (RDI) of pazopanib and its relationship with treatment outcomes and health-related quality of life will be assessed.

## 1. INTRODUCTION

# 1.1. Background

Originating in the renal cortex, renal cell carcinomas (RCCs) account for 80-90% of all primary renal neoplasms [Ansari J, 2010]. Each year there are close to 200,000 new diagnoses of RCC worldwide. In both the US and the UK, the incidence of RCC increases with age, leveling off at around 70 years, and is more common in men than in women [Weikert, 2010]. In recent decades, the incidence of renal cancer has increased worldwide. It is estimated that in the US and most EU countries, the incidence of RCC is currently increasing by approximately 3% per year [Bratslavsky, 2010]. While increased incidence is partly due to better detection with improved diagnostic imaging, the increasing prevalence of RCC risk factors such as hypertension and obesity are also contributing factors [Sanford, 2010]. In terms of mortality, RCC deaths accounted for approximately 2% of cancer deaths in the US and the UK in 2008 [Kidney cancer statistics, 2010; Jemal, 2008].

For patients with clinically localized RCC, surgical resection is the mainstay treatment for curative intervention. For most patients with metastatic RCC (mRCC), treatment has traditionally involved cytokine therapy with interferon (IFN)-α or interleukin-2 (IL-2), due to the resistance of metastatic RCC to chemotherapy, radiotherapy and hormone therapy [Hutson 2011]. Cytokine therapy is less than ideal, however, with response rates between 10-20% and well-established toxicity [Clark, 2010].

In 2004, targeted therapies for metastatic RCC that have produced substantial gains in the management of metastatic RCC first became available. These advances in the treatment of RCC came from the recognition that RCC is a compilation of several histological subtypes caused by different genetic mutations that occur with varying incidences. Clear cell carcinoma, which accounts for approximately of 75% of RCC cases, is by far the most common histological subtype and the most widely studied. Other subtypes include papillary (12%), chromophobe (4%), oncocytoma (4%), collecting duct (<1%), and unclassified (3-5%) [Lang, 2010]. The pathogenesis of clear cell RCC often involves the mutation of the von Hippel-Lindau (VHL) protein, leading to high levels of hypoxia-inducible factor alpha (HIF $\alpha$ ), which, in turn, leads to abnormal activation of vascular endothelial growth factor (VEGF), platelet-derived growth factor (PDGF), and transforming growth factor alpha (TGF $\alpha$ ).

Angiogenesis, the process of new blood vessel formation, plays an important role in the development of malignancy as well as the growth and progression of metastatic lesions. The molecular pathways involved in angiogenesis have been targeted for anti-tumor therapy which aim to either block the pathways that regulate HIF $\alpha$  levels, directly inhibit the function of VEGF, or interrupt signaling downstream from the VEGF receptor via tyrosine kinase inhibitors (TKIs). The TKIs inhibit VEGF and PDGF receptors on cancer cells, vascular endothelial cells, and pericytes, stopping the proliferation of tumour cells and the development of tumour blood vessels. One of the first oral TKIs made commercially available as a first line treatment for mRCC in 2006 was sunitinib (Sutent, Pfizer). Although sunitinib is considered an effective treatment, it is associated with a number of adverse events as a result of its toxicity (including hypertension, fatigue, diarrhoea, and hand-foot syndrome) [Schwandt, 2009], which can lead to substantial issues such as incomplete dosing or complete discontinuation.

VOTRIENT™ (pazopanib), a recently approved TKI, is a potent, selective, multitargeted inhibitor of VEGF receptors (VEGFR) 1, 2, and 3; PDGF receptors α and β; and stem cell factor receptor (c-Kit) [Sonpavde, 2007; Sonapavde, 2008]. It has been demonstrated to be a more selective kinase inhibitor than sunitinib with a higher binding affinity for VEGFR-2 in vitro [Karaman, 2008; Kumar, 2009]. In a pivotal Phase 3, randomized, double-blind trial [VEG105192], pazopanib when compared with placebo showed a statistically significant improvement in median progression-free survival (PFS) of approximately 8 months (10.8 versus 2.9 months [Independent Review Committee assessment, HR 0.36, 95% CI 0.24 to 0.55]) [Sternberg, 2010]. Pazopanib was associated with a significant improvement in objective response rate (ORR: complete response [CR] + partial response [PR]) compared with placebo (32% vs. 4%; p<0.001) as well as a clinically relevant reduction in risk of death. The most commonly reported adverse events in patients treated with pazopanib during the study were diarrhoea, hypertension, hair color changes, nausea, anorexia, vomiting and fatigue [for additional details, refer to local labeling for pazopanib].

Clinical data indicate that pazopanib is absorbed after oral administration and is generally well-tolerated at the 800 mg daily dosing regimen, its daily dosing regimen is an active monotherapy dose for patients with cancer (providing optimal biologic and clinical effects associated with VEGFR inhibition) and has encouraging efficacy in specific tumor settings such as RCC, sarcoma, non-small cell lung cancer, cervical and ovarian cancer. Additional supportive data specifically in RCC are available from a Phase 2 study [VEG102616] and the open-label extension study to the Phase 3 [VEG107769] [Hutson, 2010]. Consistent with the Phase 3 results, the response rate in VEG102616 was 34% in treatment-naive subjects and was 32% in VEG107769 (all subjects). Median PFS in these studies was similar to that reported in VEG105192. Qualitative and formal indirect evaluation of data from the pivotal clinical trials suggests that pazopanib has a favourable safety profile in comparison to other TKIs, predominantly in relation to haematological AEs, cardiotoxicity, and events that can affect patients' daily functioning and quality of life such as hand-foot syndrome, mucositis, stomatitis, and fatigue [NICE, 2010].

A head-to-head non-inferiority trial of pazopanib versus sunitinib in patients with locally advanced and/or metastatic RCC (COMPARZ, or "Comparing the efficacy, safety, and tolerability of pazopanib vs sunitinib") [VEG108844] is ongoing. The primary endpoint is PFS; secondary endpoints include overall survival, duration of response, quality of life, medical resource utilisation and safety assessments. In addition, there is an ongoing randomized, double-blind, cross-over study of pazopanib versus sunitinib [VEG113046], which is meant to assess how the tolerability and safety differences between each drug translate into patient preference (PISCES, or "Patient preference study of pazopanib versus sunitinib in advanced/metastatic RCC"). Pazopanib was approved in the US in 2009 and conditionally approved in the EU in 2010 for treatment of advanced RCC.

# 1.2. Study Rationale

Although the recently available targeted therapies have provided important improvements in disease prognosis, for some therapies adverse effects may limit tolerability and substantively impact patient quality of life. The availability of alternative treatments that

# 2011N118677\_00 **CONFIDENTIAL** VEG115232

offer similar (or improved) effectiveness with a more favourable safety and tolerability profile remains an unmet need for patients with advanced/metastatic RCC.

While the safety and efficacy of pazopanib has been evaluated in the pivotal randomized, double-blind, placebo-controlled, multinational trial and other clinical studies, real-world data are needed to further evaluate the safety, tolerability and effectiveness of this more selective TKI therapy. The purpose of the PRINICIPAL study is to evaluate the real world effectiveness and safety of pazopanib in patients with advanced and/or metastatic predominantly clear cell RCC..

# 2. OBJECTIVES AND ENDPOINTS

Objectives	Endpoints
Primary	
The primary objectives of the study are:	
To evaluate overall survival (OS), progression-free survival (PFS) and the overall response rate (ORR) in patients treated with pazopanib	PFS: defined as the interval between the date of first treatment with pazopanib and the earliest date of disease progression (by tumour response assessed by imaging or by clinical deterioration, whichever comes first) or death due to any cause OS: defined as the time from first treatment with pazopanib until death due to any cause ORR: defined as the percentage of patients with documented response (CR or PR) at any time during follow-up
2. To characterize the relative dose intensity (RDI) and its observed effect on treatment outcomes	Study population distribution of RDI
3. To characterise the RCC patient population treated with pazopanib (e.g., by demographics, disease characteristics, previous RCC treatment history) in comparison to a selected clinical trial population	Study population distribution of baseline characteristics
To evaluate the change in health-related quality of life (HRQoL) relative to baseline in patients treated with pazopanib	Change from baseline
5. To evaluate the frequency of serious adverse events (SAEs) and adverse events of special interest (AESIs) in patients treated with pazopanib	Any adverse event that results in a pazopanib dose modification or discontinuation Evidence of liver toxicity (e.g., increased ALT and/or AST, liver failure) New onset or worsened hypertension Cardiac dysfunction (e.g., decreased left ventricular function, congestive heart failure) Thyroid dysfunction
Secondary	
1.To evaluate clinical effectiveness, safety and RDI in those patients with comparable baseline characteristics to those included in the Phase III clinical trial [VEG105192]	Same as primary effectiveness, safety and RDI objectives.
2. To evaluate clinical effectiveness, safety, RDI and HRQoL in relevant subgroups treated with pazopanib	Same as primary effectiveness, safety, HRQoL and RDI objectives.

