# 4.2. Permanent Discontinuation from Study Treatment and Patient Completion Criteria

# 4.2.1. Permanent Discontinuation from Study Treatment

Patients will receive pazopanib at the discretion of the treating physician (e.g., until disease progression, death or unacceptable adverse event). The primary reason study treatment was permanently discontinued must be documented in the eCRF.

If the patient voluntarily discontinues from treatment due to toxicity, 'adverse event' should be recorded as the primary reason for permanent discontinuation in the eCRF.

All patients who permanently discontinue study treatment should be followed for progression, survival and new therapies according to the protocol schedule, for up to 30 months post-enrollment.

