#### 7.3. Effectiveness

#### 7.3.1. Effectiveness Endpoints

The primary effectiveness endpoints of this study are:

- Overall survival (OS): defined as the time from first treatment with pazopanib until death due to any cause;
- Progression free survival (PFS): defined as the interval between the date of first treatment with pazopanib and the earliest date of disease progression (by tumour response assessed by imaging or by clinical deterioration, whichever comes first) or death due to any cause;
- Overall Response Rate (ORR): defined as the percentage of patients with documented response [complete response (CR) or partial response (PR)] at any time.

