# 9.2.4. Key Elements of Analysis Plan

The demographic and clinical profile of the study population will be described using baseline data. Continuous variables (e.g., age) will be reported as means, medians, ranges and standard deviations, as appropriate. Categorical variables (e.g., gender, race/ethnicity) will be summarized as number and percentage (%) of the total study population. Statistical analyses will be fully described in the written statistical analysis plan RAP. Evaluations and interpretations will be based on point estimates and 95% confidence intervals (CI) as evaluation of the statistical precision around the point estimate, where relevant. Effectiveness and safety analyses will be stratified by patient risk category, performance status (ECOG) and age (< 65 and  $\ge$  65 years) at enrollment, where relevant. Analyses may be additionally stratified by prior treatment, history of nephrectomy, histologic subtype and other characteristics as appropriate and as the distribution of characteristics allow. No formal hypothesis or statistical significance testing is planned. This approach follows the *Guidelines for Good Pharmacoepidemiology Practices*, Section D, point 10.

Data will be listed and summarized according to the GSK reporting standards, where applicable. Complete details will be documented in the RAP. Any deviations from, or additions to, the original analysis plan described in this protocol will be documented in the RAP and final study report.

As it is anticipated that accrual will be spread thinly across centers and summaries of data by center would be unlikely to be information, data from all participating centers will be pooled prior to analysis. All data up to the time of study completion/withdrawal from study will be included in the analysis, regardless of duration of treatment. There will be no imputation for missing data.

For the analysis of overall survival, the last date of known contact will be used for those patients who have not died at the time of analysis; such patients will be considered censored.

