Progression will be determined by tumour response assessed by imaging or by clinical deterioration, whichever comes first, and regardless of whether treatment was discontinued or modified. For the analysis of PFS, if the patient received subsequent anticancer therapy prior to the date of documented progression or death, progression free-survival will be censored at the last adequate assessment (e.g., assessment where visit level response is complete response, partial response or stable disease) prior to the initiation of therapy. Otherwise, if the patient does not have a documented date of progression or death, progression-free survival will be censored at the date of the last adequate assessment. Further details on rules for censoring will be provided in the RAP.

Details on the determination of tumour response are given in Appendix 2. Additional details on effectiveness analyses are provided in Section 9.2.4.1. Similarly additional details on safety analyses are provided in Section 9.2.4.1.

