#### 6. Evaluation of best overall response

The best overall response is the best response recorded from the start of the treatment until disease progression/recurrence and will be determined programmatically by GSK based on the investigators assessment of response at each time point.

- To be assigned a status of SD, follow-up disease assessment must have met the SD criteria at least once after first dose at a minimum interval of 56 days.
- If the minimum time for SD is not met, best response will depend on the subsequent assessments. For example if an assessment of PD follows the assessment of SD and SD does not meet the minimum time requirement the best response will be PD. Patients lost to follow-up after an SD assessment not meeting the minimum time criteria will be considered not evaluable.

2011N118677\_00 **CONFIDENTIAL** VEG115232

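### The ORR definition sets no end to the response window, conflicts with Appendix 2, and nowhere stops at a new anticancer therapy started before progression

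*Protocol*

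**What the plan says.** ORR is one of three primary effectiveness endpoints. The protocol describes its time window in several places.

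- **Endpoint definitions.** Section 2: "ORR: defined as the percentage of patients with documented response (CR or PR) at any time during follow-up". Section 7.3.1 counts a "documented response [complete response (CR) or partial response (PR)] at any time", and the Protocol Summary (Study Assessments) agrees. None of the three names a closing date.
- **Follow-up after pazopanib.** Under Section 4.2.1, patients who stop treatment "should be followed for progression, survival and new therapies according to the protocol schedule, for up to 30 months post-enrollment". Section 7.2 lists tumour response status and additional RCC treatments among the follow-up data, without limiting response to time on pazopanib.
- **Data used.** Section 9.2.4: "All data up to the time of study completion/withdrawal from study will be included in the analysis, regardless of duration of treatment".
- **ORR analysis.** Section 9.2.4.1.1 fixes the assessor (investigator), the population (measurable disease, MD) and the handling of missing response, but no window.
- **Appendix 2, item 6.** "The best overall response is the best response recorded from the start of the treatment until disease progression/recurrence"; the sponsor is to derive it by program. The opening of Appendix 2 presents its content as reference material with nothing mandated, yet Section 9.2.4 sends the reader there for how tumour response is determined.
- **PFS.** Section 9.2.4 has a rule that applies "if the patient received subsequent anticancer therapy prior to the date of documented progression or death": PFS is then censored at the last adequate assessment before the new therapy. The sentence covers PFS only.
- **Duration of response.** Section 9.2.4.1.2 applies the PFS censoring rules.

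**The concern.** The endpoint definitions and Appendix 2 give different windows for the same primary endpoint. A programmer who follows Section 2 would count a first CR or PR seen on a second-line drug after progression. A programmer who follows Appendix 2 would not.

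A second gap remains whichever text is followed. A patient who leaves pazopanib without progressing, for example for toxicity, and then responds to another drug is a responder under both. For PFS the protocol recognises this situation and cuts it off; for ORR it does not.

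What is at stake is attribution. The stated objective is response in patients treated with pazopanib, but part of the reported figure could reflect a treatment sequence. A confidence interval does not cover an error of this kind.

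**Working it through.** **1. The windows side by side**

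| Source | Opens | Closes at progression? | Closes at new therapy before progression? |
|---|---|---|---|
| Summary, Sections 2 and 7.3.1 | not stated | no | no |
| Section 9.2.4.1.1 (ORR) | not stated | not stated | not stated |
| Appendix 2, item 6 | start of treatment | yes | no |
| Section 9.2.4 (PFS) | first dose (Section 7.3.1) | event | yes, by censoring |

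The first and third rows conflict. The last column is empty of any stop for ORR. Of the five sensitivity analyses in Section 9.2.4.1.1, only the fifth names ORR, and it deals with missing response. The fourth uses the start of new therapy only as a progression date.

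There is also a mismatch within the plan. If a response is first seen on a later drug, with no earlier progression, the patient counts in ORR. Under the PFS rules, the censoring date for duration of response then falls before the response began.

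**2. The plan's own precision figures**

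Section 9.1.1 uses p = 0.30 and the normal approximation: N = 1.96² × 0.30 × 0.70 / h², rounded up.

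- h = 0.10: 81
- h = 0.05: 323
- h = 0.04: 505
- h = 0.03: 897

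All four match the protocol. At N = 700 the half-width is 1.96 × √(0.30 × 0.70 / 700) = 0.0339, or 3.4 points, which agrees with the stated precision of less than 4%. ORR is analysed in the MD population, whose size is not given. If 70%, 80% or 90% of 700 have measurable disease (assumed), the half-width is 4.1, 3.8 or 3.6 points.

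**3. Possible size of the effect**

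Let p be the true pazopanib ORR (0.30, the planning value). Let f be the share of pazopanib non-responders who are assessed on a later drug inside the counting window, and r their CR/PR rate on it. Then

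reported ORR = p + (1 − p) × f × r, so the excess = 0.70 × f × r.

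The documents give neither f nor r. Both are assumptions, shown over a range. Excess in percentage points:

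*Appendix 2 cut-off applied, so only switches before progression count*

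| f | r = 5% | r = 10% | r = 20% | r = 30% |
|---|---|---|---|---|
| 5% | 0.2 | 0.35 | 0.7 | 1.05 |
| 10% | 0.35 | 0.7 | 1.4 | 2.1 |
| 20% | 0.7 | 1.4 | 2.8 | 4.2 |

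*Literal definition, no cut-off*

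| f | r = 5% | r = 10% | r = 20% | r = 30% |
|---|---|---|---|---|
| 20% | 0.7 | 1.4 | 2.8 | 4.2 |
| 40% | 1.4 | 2.8 | 5.6 | 8.4 |
| 60% | 2.1 | 4.2 | 8.4 | 12.6 |

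The excess equals the planned half-width when f × r = 0.0339 / 0.70 = 0.048. With the progression cut-off, only the top corner of the assumed range exceeds that. Without it, much of the range does.

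**The case against.** The best defence is that Appendix 2 already governs. Section 9.2.4 refers to it for tumour response, item 6 describes what the sponsor itself will program, and the reference-only disclaimer reads most naturally as addressed to sites choosing how to assess disease. On that reading, responses after progression are excluded. This is a fair reading and may be the intended one. It stands to this extent: a reader might infer from Section 2 that every response on a later drug up to month 30 will be credited to pazopanib, and the documents do not support so flat a statement. What the defence does not do is remove the contradiction with three endpoint definitions, or supply a stop at a new drug begun before progression.

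Other points on this side:

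- The 30 months run from enrollment, not from the end of pazopanib, so time on later drugs is shorter than a reader might assume. Section 4.2.1 also does not name response among the items followed after discontinuation, although the general list in Section 7.2 does not exclude it. Both points stand.
- The 30% from VEG105192 is a planning proportion. A reader might infer that ORR will be tested against it, but Section 9.2.2.1 states no treatment comparisons and Section 9.2.4 no formal testing. This stands and lowers the severity.
- Net bias in ORR is not shown to be upward, because missing responses count as non-responses, which pulls the other way. This stands; only the mechanism described here is one-directional.
- Endpoints may legitimately treat later therapy differently, as OS does by its nature, and the analysis plan, which is not shown, may add a cut-off. That is possible, but the protocol itself states two different windows, so the conflict cannot be put down to detail left for later.

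**Conclusion.** The point holds in limited form, with moderate severity. The protocol gives two incompatible windows for a primary endpoint without saying which prevails, and no visible text stops the ORR count at a new anticancer therapy started before progression. Responses to a later drug can therefore be counted as pazopanib responses. Whether they will be, and how many, cannot be established from the documents.

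On assumed inputs the effect is about +0.2 to +4.2 points if the progression cut-off applies (f 5–20%, r 5–30%) and about +0.7 to +12.6 points on the literal wording (f 20–60%, r 5–30%). The smaller range is the relevant one if Appendix 2 is meant to govern, and it lies mostly below the planned half-width. The direction of this mechanism does not depend on the inputs, since a later response can only add a responder.

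**What to change.** Use one definition in the Protocol Summary and in Sections 2, 7.3.1 and 9.2.4.1.1: ORR is the percentage of MD patients with a CR or PR recorded from first pazopanib dose up to the earlier of (a) documented progression and (b) start of any subsequent anticancer therapy. Put the same window in Appendix 2, item 6, and state that this rule governs the analysis whatever the reference status of the rest of the appendix.

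This is an analysis rule and changes nothing in patient care or data collection. Dated assessments (Section 3), progression dates and additional RCC treatments (Section 7.2) are already collected, and the PFS censoring rule already needs the start of new therapy. The cost is a short text amendment and a reported ORR that may be slightly lower.
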